9.0 Risks and Benefits

9.1 Describe and assess any potential or known risks and discomforts, including possible loss of confidentiality, and assess their likelihood and seriousness. Also describe precautions to decrease the likelihood of harm and procedures to deal with harms if they occur. NOTE: Risks or harms can be physical, financial, social, or legal. They may involve breaches of

confidentiality and privacy. Do not include the risks of usual care unless usual care is part of the research interventions being performed.

Physical

A low carbohydrate diet may cause side effects, particularly during the first several weeks. These include:

1. Constipation: this is a common side effect, which will be managed by instructing individuals to increase their consumption of water and low-carbohydrate, fiber-rich foods such as leafy greens.
2. Headaches: this is a likely side effect, which will be managed by instructing individuals to increase their water and salt consumption.

There is also a small risk patients may experience harm or injury if they increase their physical activity as a result of taking part in this program.

Psychological - (For Example: Loss of privacy and confidentiality may cause psychological issues.)

There is a potential risk of loss of data confidentiality, which could have psychological risks. We will mitigate this risk by using a secure, HIPAA compliant, crosswalk file linking participant IDs and direct identifiers.

Participants may be concerned about their risk for developing type 2 diabetes. We will ease their anxiety by emphasizing that type 2 diabetes is a preventable condition and that this intervention is one way to help them to reduce their risk.

Social and economic - (For Example: Loss of confidentiality may cause social or economic duress though the unlikely risk is low.)

There is a potential risk of loss of data confidentiality, which could have social or economic consequences, although this risk is low.

9.2 Describe any risk of discovering abnormal findings and how you will inform the subject and/or the subject's primary care provider.

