13.9 VA SENSITIVE DATA (VASI)

13.10 Please describe your use of VA Sensitive Information (VASI):

- This protocol does not collect or use VASI
- This protocol uses, but does not save, collect, copy, or record VASI.
- This protocol collects, records, or saves VASI.

In which of the following ways will VASI be accessed/collected?

- Computer access
- Medical chart review
- Patient treatment
- Personal interviews
- Other

Please give a brief description of the data sources mentioned above and how they will be accessed.

Medical charts will be used to identify patients who meet study eligibility criteria and also to order and record laboratory tests (i.e., HbA1c, lipid panel). Study participants will be invited to take part in optional semi-structured interviews at 6 and 12 months. Participants will complete surveys at baseline, 6 months, and 12 months; these surveys will include self-reported side effects and experiences with the intervention.

13.11 Indicate the type of PII to be accessed. If you requested a HIPAA waiver for screening only, indicate any additional PII types that will be used post-screening.

- Names
- Any geographic area smaller than a state
- Any date (except year) that is directly related to an individual and/or ages over 89
- Telephone numbers
- Fax numbers
- Email addresses
- Social Security Numbers (SSNs) or Scrambled SSNs
- Medical record numbers
- Health plan beneficiary numbers
- Account numbers
- Certificate and/or license numbers
- Vehicle ID and serial numbers including license plate numbers
- Device identifiers and serial numbers
- Web Universal Resource Locators (URLs)
- Internet protocol (IP) addresses
- Biometric identifiers, including finger & voice prints
- Full-face photographic images and any comparable images
- Any other unique identifiers (number, characteristic, or code)
- None of the above

Please explain the other unique identifier(s).

Other identifier is CDW PatientICN. Biometric identifiers refer to voice recordings collected during interviews.

13.12 Will this protocol include the use of Protected Health Information (PHI) that requires specific consent from subjects? If you requested a HIPAA waiver for screening only, indicate any PHI types that will be used post-screening.

- Alcoholism or alcohol abuse information
- Drug abuse information
- Sickle cell anemia information
- HIV test/infection results
- None of the above

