We will recruit up to 30 veterans with prediabetes to participate in the LC-DPP. The intervention will be delivered in partnership with VA Certified Diabetes Educators who will serve as lifestyle coaches for the group-based intervention. The LC-DPP lifestyle coaches will deliver 16-weekly one-hour group sessions over the first 6 months and 8 maintenance sessions over the subsequent 6 months. **Table 1** shows session topics. Participants will receive a binder to hold study materials. They will be provided with printed handouts on a session-by-session basis. Individuals that are absent for a particular session will receive corresponding session materials by e-mail or postal mail.

The CDC's Diabetes Prevention Program instructs participants to adhere to a fat-restricted diet with an explicit cap of less than 33-55 grams of fat per day depending on starting body weight. In contrast, LC-DPP participants will be initially instructed to follow *ad-libitum* very low-carbohydrate diet, which restricts carbohydrate intake (not including fiber) to 20-35 grams per day with the goal of achieving nutritional ketosis. Participants will be encouraged to eat a normal amount of protein (roughly 80-120 grams per day) and to derive the remaining calories from fat. Allowable foods include: meats, fish, poultry, eggs, cheese, seeds, nuts, leafy greens, non-starchy vegetables, and some fruits.

During the LC-DPP's maintenance phase, participants will be instructed to gradually reintroduce carbohydrates (e.g., 5 non-fiber grams of carbohydrates per week) if: (1) they have met their weight loss target and (2) if they desire to liberalize their carbohydrate intake.

To minimize potential side effects (e.g. headache, constipation, muscle cramps, diarrhea, general weakness, and rash) participants will be instructed to replace one meal a week with a low-carbohydrate alternative, starting with breakfast. Participants will be counseled to drink sufficient water and to consume adequate sodium. Further, primary care providers will be notified of their patients' involvement in this study, and they will be given a handout that describes the intervention, potential side effects, and strategies to minimize side effects.

Session Number	Topic
Core phase	
0	Study information session (Informed consent to be obtained)
1	Welcome to the Low-Carb Diabetes Prevention Program
2	Be a Carbohydrate Detective
3	Low-Carb Meals
4	Low-Carb Cooking and Shopping
5	Move Those Muscles

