 - The researchers will minimize this risk by compensating participants for the time required to complete the surveys at 6 and 12 months and to complete blood draws at 0, 6, and 12 months.
- Blood draws:
 - Adverse effects of blood draw may include lightheadedness, dizziness, bruise or infection at blood draw site.
 - If participants experience any adverse effects, we will ensure that participants receive appropriate medical care

- Questionnaires:
 - Some of the questions may make participants feel uncomfortably or upset. All participants are free to decline to answer any questions they do not wish to answer and to discontinue participation at any time.
- Diet:
 - Participants may experience some side effects when first reducing the amount of carbohydrates in the diet. This may include constipation, headache, bad breath, and muscle cramps. These symptoms usually go away after the first couple weeks on the diet. Participants can speak with study staff and study physicians ([name]). We have also shared information with participants' primary care providers regarding the benefits and potential side effects of low-carbohydrate diets.
- Increase in physical activity:
 - Participants may experience harm or injury from exercise if they increase their physical activity as a result of participation. As there is no requirement for patients to engage in physical activity as part of this study and no physical activity will be encouraged other than that ordinarily encountered in daily life, we do not consider the risk to be above minimal. Participants will be encouraged to contact the study team and/or their PCP in the event of any adverse events.

As with any research study, there may be additional risks that are unknown or unexpected. We do not know if participants will get any benefits from taking part in this research study. However, possible benefits may include weight loss, decreased risk of diabetes, reduction in hemoglobin A1c. Participation in this study may also help the study team to design and test new ways to help more people prevent type 2 diabetes.

Participants will receive results of a hemoglobin A1c and cholesterol tests at 6 and 12 months.

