5.5 Study Evaluations

Quantitative Data source

a) Weight

Participants will be encouraged to self-monitor weight using a home scale although this

data will not be collected by the study team. In accordance with standard DPP operating procedure, participants will be weighed in a private room prior to each session and their weight will be recorded by a member of the study team.

b) Physical activity

In accordance with standard DPP operating procedure, participants will be encouraged to self-monitor physical activity minutes and to report this information to the lifestyle coach at the start of each session.

c) Laboratory metrics

We will evaluate change in A1c and lipids over the study period. Baseline laboratory studies will be obtained once individuals have consented to participate in this study. Repeat A1c and lipid levels will be drawn at 6 and 12 months.

d) Session attendance

Participants will be encouraged to attend all sessions and attendance will be recorded by the lifestyle coach.

e) Survey Data

At baseline, 6 months, and 12 months, study participants will be invited to complete a written survey. Paper copies will be given to individuals at session 15/16. Because we aim to obtain complete follow-up data, we will make efforts to collect survey responses from participants that are not present for session 15/16. We will send surveys to non-attendeess via postal mail. All individuals will be asked to return their survey to the study team via pre-paid envelope or in-person delivery. The survey will assess domains related to the following: global health and well-being; sleep; food cravings; stress eating; hunger; energy; mood; physical symptoms, neuropathic symptoms (e.g., tingling, burning in feet); side effects; and cost of food. At baseline, we will ask participants to provide sociodemographic characteristics. At 6 months and 12 months, participants will be asked to provide feedback about the study and will receive compensation for each survey.

Qualitative Data Sources

Participants will be encouraged to maintain a log of food intake and physical activity. Each week, the lifestyle coach will review the logs and provide individual feedback. We will retain copies of participants' logs from their first 2 weeks in the study and their last 2 weeks in the study. In this way, we can qualitatively assess changes in dietary habits and physical activity.

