Change in body weight: Body weight will be measured and recorded at each attended session. We will calculate average body weight change and percent body weight loss at the end of the program's core phase (6 months) and maintenance phase (12 months). Among session non-attendees, we will attempt to schedule 6- and 12-month weigh-ins at participants' convenience within 2 weeks of the final core and maintenance sessions. All weights will be obtained using the same calibrated scale.

Change in HbA1c: We will calculate change in HbA1c from baseline to 6 and 12 months

Change in lipids: We will calculate change in triglycerides and total cholesterol/HDL ratio from baseline to 6 months and 12 months.

Change in survey measures: We will calculate change in self-reported survey measures from baseline to 6 months and 12 months.

Fidelity: We will measure intervention fidelity (i.e., extent to which components of an intervention are delivered as intended) using quantitative measures adapted from the literature²⁶ as well as qualitative interview feedback from participants and dietitians.

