Below is a list of reasons that people sometimes give for eating tasty foods and drinks such as:

- Sweets like chocolate, doughnuts, cookies, cake, candy, ice cream, other desserts.
- Salty snacks like chips, pretzels, and crackers.
- Fast foods like hamburgers, cheeseburgers, pizza, fried chicken and French fries.
- Sugary drinks like soda, sweet tea, milkshakes, and smoothies.

To forget y	Q3	1 =	Coping	Burgess,
Because it	Q4	Almost	score:	E. E.,
To cheer u	Q5	never/Ne	Average	Turan, B.,
To forget a	Q6	ver	of four	Lokken, K.
		2 = Some	responses	L., Morse,
		of the	.	A.. &

Energy Levels between Meals

In the past week, two hours after you ate BREAKFAST, how do you feel?

Alert	Q1	Answer	NA	NA
Energetic	Q2	choices 1		
Tired	Q3	through		
Brain fog o	Q4	7, with		
Food cravii	Q5	anchors		
Hunger	Q6	on 1, 7:		
Moodiness	Q7	1- Not at		
		all		
		7		

In the past week, two hours after you ate LUNCH, how do you feel?

Alert	Q8	Answer	NA	NA
Energetic	Q9	choices 1		
Tired	Q10	through		
Brain fod o	Q11	7, with		
Food cravii	Q12	anchors		
Hunger	Q13	on 1, 7:		
Moodiness	Q14	1- Not at		
		all		

Physical Symptoms

How often have you experienced the following over the past week?

Acne	Q1		NA	NA
Bad breath	Q2			
Bloating or	Q3			

Cold hands Q4
Constipation Q5
Diarrhea Q6
Dizziness Q7
Dry mouth Q8
Constant tiredness Q9
Food intolerance Q10

Headaches Q11

Heart palpitations or a racing heart Q12

Heartburn Q13

Joint or muscle pain Q14

Muscle cramps Q15

Nausea Q16

Trouble concentrating Q17

Weakness Q18

Hair loss Q19

Sexual problems Q20

Numbness (loss of sensation) in the feet, legs, or hands Q21

Tingling or prickling sensation in the feet, legs, or hands Q22

Not at all
1 day a week
2-3 days a week
4-5 days a week
6-7 days a week

Burning or shooting pain in the feet, legs, or hands

Q23

Blurred or deteriorating vision

Q24

Please describe any other psychological or physical symptoms that you experienced during the past month.

Q25

Participants may enter free text of whatever they choose.

Health
Global Health PROMIS Questionnaire:

Please respond to each item by marking one box per row

In	Q1	5-	Re-code:	PROMIS
In	Q2	Excellent	Q7 (pain	Health
general,		4- Very	on	Organizati
would		good	average):	on and
you say		3- Good	0 = 5	PROMIS
your		2- Fair	1,2,3 = 4	Cooperati
quality of		1- Poor	4,5,6 = 3	ve Group,
life is:			7,8,9 = 2	2008-
In	Q3		10 = 1	2012.
general,				https://w
how			Global	ww.iconq
would			Physical	uerms.org
you rate			Health	/sites/all/

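### Side effects are expected in the first weeks of the diet, but the past-week symptom checklist is first given on diet at session 15/16, so it cannot estimate them

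*Protocol*

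**What the plan says.** **When side effects are expected.** The Diet entry under Risks and Benefits (narrative section 5.1) ties constipation, headache, bad breath and muscle cramps to the first reduction in carbohydrate and adds: "These symptoms usually go away after the first couple weeks on the diet". Item 9.1 of the IRB application says: "A low carbohydrate diet may cause side effects, particularly during the first several weeks".

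**That they will be measured.** Item 13.10 of the application says of the surveys at baseline, 6 and 12 months that "these surveys will include self-reported side effects and experiences with the intervention". Narrative section 5.5 e) lists physical symptoms and side effects among the survey domains.

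**How and when.** The Physical Symptoms table in the SAP has 24 structured items under the question "How often have you experienced the following over the past week", plus one free-text item about the past month. The baseline survey follows consent, before the first class. For the next survey, section 5.5 e) says: "Paper copies will be given to individuals at session 15/16". Absentees are mailed a copy.

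**How it is analysed.** Section 5.5, Secondary Measures: "We will calculate change in self-reported survey measures from baseline to 6 months and 12 months". Section 5.6 and the SAP give the same time points.

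**What happens at the early classes.** Section 5.5 schedules weight, attendance, activity minutes and review of food and activity logs. It schedules no symptom question.

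**The concern.** The measurement misses the period that the plan itself identifies as the risk period. Two further features push the late result towards apparent tolerability. Under item 9.7 of the application nothing is collected after withdrawal, so anyone who leaves because of early side effects gives no later checklist. The same item lets people who stop the diet stay enrolled, so some 6-month answers will describe people who are off it.

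The pilot is meant to improve the curriculum and inform a large comparative trial. The narrative names side effects as a possible barrier to adherence, and they shaped the phased start and the water and sodium advice. A finding of no change in symptoms at 6 months could be read as good tolerability. The later trial would have no early frequency of any named side effect for its consent wording, coach guidance or safety monitoring.

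**Working it through.** The documents give no figure on this point to reproduce. The check compares the expected side-effect period with the recall windows of the checklist.

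**Inputs from the documents**
- Side effects last a couple of weeks (narrative 5.1) or several weeks (item 9.1).
- The diet is phased in one meal at a time, weekly, starting with breakfast (narrative 5.1, Intervention).
- There are 16 core classes, described both as weekly and as covering the first 6 months (narrative 5.1). Session 16 is treated as the 6-month point (item 6.26).
- Checklist recall is one week; the free-text item covers one month (SAP).
- Enrolment is up to 30. A 10% yield from 220 letters would give 22.

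**Assumptions.** Session 1 is in week 1. Phase-in takes 0 weeks (immediate start) or 3 weeks (one meal type a week, three meals a day). Symptoms then last 2 to 6 weeks.

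**End of the early period** = 1 + phase-in + symptom duration
- Shortest: 1 + 0 + 2 = week 3
- Longest: 1 + 3 + 6 = week 10

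**First on-diet checklist window**

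| Class schedule | Survey at | Week | Past-week window |
|---|---|---|---|
| Weekly | session 15 | 15 | 14–15 |
| Weekly | session 16 | 16 | 15–16 |
| Spread over 26 weeks | session 15 | 1 + 14 × 25/15 = 24.3 | 23.3–24.3 |
| Spread over 26 weeks | session 16 | 26 | 25–26 |

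**Gap** = start of window − end of early period
- Weekly classes, session 15: 14 − 10 = 4 weeks to 14 − 3 = 11 weeks
- Classes spread out, session 16: 25 − 10 = 15 weeks to 25 − 3 = 22 weeks

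No combination overlaps. The past-month free-text item opens at 15 − 4.3 = week 10.7 at the earliest, so it also misses, though by only 0.7 weeks in the most favourable case.

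**Coverage.** The two on-diet checklists cover 2 of 52 weeks (3.8%) and none of the first 8. Past-week forms at weeks 2, 4, 6 and 8 would cover 4 of the first 8.

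**Illustration for one symptom (rates assumed, not in the documents).** Cases still visible at the survey = 30 × p × (1 − r), where p is the early incidence and r the share resolved.
- p = 0.20: 6 early cases; r = 0.80 leaves 1.2, r = 1.00 leaves 0
- p = 0.50: 15 early cases; r = 0.80 leaves 3, r = 1.00 leaves 0

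This assumes that everyone returns the survey; non-response and withdrawal lower the count further.

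**What early forms would give, per symptom (Clopper-Pearson 95% CI, everyone assessed)**

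| Observed | Estimate | 95% CI |
|---|---|---|
| 6/30 | 20% | 7.7–38.6% |
| 9/30 | 30% | 14.7–49.4% |
| 4/22 | 18% | 5.2–40.3% |
| 7/22 | 32% | 13.9–54.9% |

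If a symptom truly affects 10%, the chance of seeing it at least once is 1 − 0.9^30 = 95.8% with 30 people, or 1 − 0.9^22 = 90.2% with 22.

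**Why symptoms should not be pooled.** Suppose each item worsens by chance with probability 5%, independently (assumed). Then at least one of 7 items is positive in 1 − 0.95^7 = 30% of people, and one given item is positive at least once over four classes in 1 − 0.95^4 = 19%. One item at one class stays at 5%.

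**The case against.** The strongest reply is that the plan never promises an early side-effect rate. Survey change is defined as baseline to 6 and 12 months, and that is what will be computed. The checklist also looks like a general health inventory: it includes acne, hair loss and neuropathy items, and neuropathy over 12 months is a stated secondary outcome that late timing suits.

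Other routes can pick up early effects:
- the survey item on what got worse on the food plan, which has no past-week limit;
- interviews at 6 and 12 months (14 participants in the narrative, up to 30 in the application);
- documented reasons for withdrawal;
- adverse event reporting under item 9.10.

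The diet-difficulty and cheating items and the retained food logs would help separate on-diet from off-diet answers.

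Part of this stands. The plan's outcomes can all be computed as written, and early effects are not wholly invisible. But these sources are recalled, unprompted or indirect, and none gives a rate with a known early denominator. The surveys are said to collect side effects, and the SAP shows no other structured symptom instrument.

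The phase-in can also be read literally as one of 21 weekly meals per week, which would run past session 15 and overlap the checklist. That conflicts with the instruction to start at 20–35 g of carbohydrate a day.

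Two criticisms of the remedy are fair. The intervals are wide. People who feel unwell and skip class will go unassessed, so the number assessed must be reported.

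**Conclusion.** The concern holds. On any sensible reading of the schedule, the structured checklist first looks at people on the diet at least 4 weeks after the expected side-effect period has ended. Its 6- and 12-month results are late symptoms in survey completers and cannot estimate early side effects.

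The lack of overlap rests on the documents' own timing plus the assumed phase-in of up to 3 weeks and symptom duration of up to 6 weeks. The case counts rest on assumed incidence and resolution rates and are illustrative only. The primary outcomes are not affected. This is a change that should be made because it is cheap and improves what the pilot can say about tolerability.

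**What to change.** 1. **Add a short early form.** Section 5.5 a) already provides that "participants will be weighed in a private room prior to each session". At the classes nearest weeks 2, 4, 6 and 8, add past-week tick-boxes for the seven effects named in narrative section 5.1: headache, constipation, diarrhea, muscle cramps, weakness, bad breath and rash. Six are already on the baseline checklist (Q11, Q5, Q6, Q15, Q18, Q2); add a rash line at baseline.
2. **Report by symptom and by class.** Give the proportion new or worse than baseline, the exact 95% CI and the number assessed. Do not pool into any symptom. Report the number withdrawing for side effects, from the reasons documented under item 9.7.
3. **Label the later results.** Describe the 6- and 12-month symptom changes as late symptoms in survey completers.
4. **If the early classes have passed,** do step 3 and code the open-ended answers and interviews for early effects.

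With one arm, the early data would describe symptoms under the phased start; they could not show that phasing reduces them.

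**Cost.** At most 4 × 30 = 120 short forms, a few minutes at each of four classes, one added baseline line and a short amendment. No new visit or staff. Absentees are counted as not assessed.
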